5. STUDY TREATMENT

5.1. Allocation to Treatment

All subjects will be allocated to receive repotrectinib in combination with trametinib. For the Phase 1b dose escalation portion of the study, subjects will be assigned according to the currently open dose level. For the Phase 2 portion of the study, all subjects will receive repotrectinib in combination with trametinib at the RP2D schedule determined in the Phase 1b portion in 28-day cycles.

5.1.1. Repotrectinib + Trametinib

Repotrectinib and trametinib will be administered orally as a combination treatment. For the Phase 1b dose escalation portion of the study, subjects will be assigned to a repotrectinib and trametinib dose according to the currently open dose level for 28 consecutive days in repeated four-week cycles. For the Phase 2 expansion portion of the study, subjects will be allocated to receive repotrectinib and trametinib at the RP2D combination determined during the Phase 1b dose-finding portion for 28 consecutive days in repeated four-week cycles.

5.2. Investigational Product Supplies

5.2.1. Dosage Form(s) and Packaging

5.2.1.1. Repotrectinib

Repotrectinib (TPX-0005) will be supplied for oral administration as 40 mg capsules. Study drug will be supplied by the Sponsor.

The investigational repotrectinib drug product is currently supplied as size 0 hard gelatin capsules of 40 mg dosage strength to deliver the active pharmaceutical ingredient, repotrectinib (TPX-0005) and has been manufactured for use in the proposed clinical study ([Table 5](#)).

Repotrectinib capsules are contained in round high-density polyethylene (HDPE) bottles with an induction seal and child resistant cap closure. The bottle does not contain a desiccant or a pharmaceutical coil.

Table 5: Investigational Product: Repotrectinib Product and Dosage Information

	Investigational Product
Product Name:	Repotrectinib
Dosage Form:	Capsules
Unit Dose:	Capsules (40 mg)
Route of Administration:	Oral
Physical Description:	Size 0 hard gelatin capsules

5.2.1.2. Trametinib

As per label ([Mekinist® \[trametinib\] USPI 2020](#)), trametinib will be supplied as commercially available in 0.5 mg or 2 mg tablets. Study drug will be supplied by the Sponsor.

Trametinib 0.5 mg tablets are yellow, modified oval, biconvex, film-coated tablets with ‘GS’ debossed on one face and ‘TFC’ on the opposing face and are available in bottles of 30 (NDC 0078-0666-15). Trametinib 2 mg tablets are pink, round, biconvex, film-coated tablets with ‘GS’ debossed on one face and ‘HMJ’ on the opposing face and are available in bottles of 30 (NDC 0078-0668-15).

Table 6: Investigational Product: Trametinib Product and Dosage Information

	Investigational Product
Product Name:	Trametinib
Dosage Form:	Tablet
Unit Dose:	Tablets (0.5 mg and 2 mg)
Route of Administration:	Oral
Physical Description (0.5 mg):	Yellow, modified oval, biconvex, film-coated tablets with ‘GS’ debossed on one face and ‘TFC’ on the opposing face
Physical Description (2 mg):	Pink, round, biconvex, film-coated tablets with ‘GS’ debossed on one face and ‘HMJ’ on the opposing face

5.2.2. Investigational Product Storage and Accountability

5.2.2.1. Repotrectinib

Repotrectinib is currently stored at controlled ambient room temperature between 15°C to 30°C. Subjects should be instructed to keep their medication in its original container and stored at 15°C to 30°C (59°F to 86°F). Returned medication should be stored separately from medication that is yet to be dispensed. The repotrectinib capsule bottle must be stored as indicated. Deviations from the storage requirements, including any actions taken, must be documented, and reported to the Sponsor.

5.2.2.2. Trametinib

The trametinib bottles are stored at controlled refrigerated temperature at 2°C to 8°C (36°F to 46°F) ([Mekinist® \[trametinib\] USPI 2020](#)). Trametinib is dispensed in the original bottle; do not remove desiccant. Protect from moisture and light. Do not place study drug in pill boxes. Returned medication should be stored separately from medication that is yet to be dispensed. The trametinib bottles must be stored as indicated. Deviations from the storage requirements, including any actions taken, must be documented and reported to the Sponsor.

5.2.3. Destruction of Investigational Product Supplies

At each cycle visit, and at the end of the treatment study, all unused or partially used bottles must be returned by subjects to the Investigator and the Sponsor will provide instructions for disposition of any unused repotrectinib or trametinib. If the Sponsor authorizes destruction at the study site, the Investigator must ensure that the materials are destroyed in compliance with

applicable environmental regulations, institutional policy, and any special instructions provided by the Sponsor. Destruction must be adequately documented.

5.3. Dose Regimen and Route of Administration

5.3.1. Repotrectinib + Trametinib

Repotrectinib and trametinib will be administered orally as a combination treatment.

For the Phase 1b dose escalation portion of the study, subjects will be assigned to a repotrectinib and trametinib dose level according to the currently open dose level (i.e., Dose Level 1, Dose Level 2, etc.) for 28 consecutive days in repeated four-week cycles.

For the Phase 2 expansion portion of the study, subjects will be allocated to receive repotrectinib and trametinib at the RP2D determined during the Phase 1b dose escalation portion for 28 consecutive days in repeated four-week cycles.

Repotrectinib and trametinib should be taken with at least 8 oz (240 mL) of water, either 1 hour before or at least 2 hours after a meal. Each dose should be taken at the same time each day. If the study drug is given BID, then the study drug should be taken in the morning, and again in the evening approximately 12 hours later.

For subjects taking repotrectinib and trametinib QD: if the subject is more than 12 hours late taking the study drug, the dose should be skipped, and the subject should continue taking repotrectinib and trametinib the next day as scheduled.

For subjects taking repotrectinib and trametinib BID: if the subject is more than 6 hours late taking the study drug, the dose should be skipped, and the subject should continue with the next scheduled dose.

5.4. Concomitant Treatments

Any concomitant medications, blood products, as well as non-drug supportive interventions (e.g., paracentesis) received by subjects from the date of signed informed consent until the EOT visit should be recorded on the appropriate electronic Case Report Form (eCRF). The Investigator should be alerted if the subject is taking any agent known to affect or with the potential for drug interactions.

Note on COVID-19 Vaccination: The use of vaccines is not a restriction for this study. Currently enrolled and potential adult clinical trial subjects are allowed to receive the COVID-19 vaccine with no impact on their eligibility or ability to remain on study treatment. This guidance will also apply to pediatric and adolescent patients once vaccine approval is available for these populations. In addition, there is not a required wash-out period for the vaccine. The risk-benefit for COVID-19 vaccination while on study should be determined by the treating physician. Administration of the COVID-19 vaccine will be recorded in the medical history or the concomitant medications CRF, as applicable, as well as any adverse events related to the vaccine.

5.4.1. Prohibited Concomitant Medications

The concomitant use of known strong CYP3A4 inhibitors is prohibited including their administration at least within 2 weeks prior to the first study drug dose and throughout the study.

Subjects should avoid grapefruit juice or grapefruit/grapefruit-related citrus fruits (Seville oranges, pomelos). Coadministration of study drug in combination with strong CYP3A4 inducers is prohibited including their administration at least within 2 weeks prior to the first study drug dose and throughout the study. See [Appendix 1](#) for a list of known CYP3A4 inhibitors and inducers.

Current or anticipated use of drugs that are sensitive CYP3A4 substrates should be avoided including their administration at least within 2 weeks prior to the first study drug dose and throughout the study. Concomitant medication suspected of being a sensitive CYP3A4 substrate must be approved by the Sponsor.

Current or anticipated use of drugs that are sensitive substrate with narrow therapeutic index for UGT1A1 should be avoided, including their administration within at least 2 weeks prior to the first study drug dose and throughout the study. Concomitant medication suspected of being a sensitive UGT1A1 substrate with narrow therapeutic index must be approved by the Sponsor.

Concomitant use of drugs that are known to be sensitive substrates with narrow therapeutic index for OATP1B1, OAT3, MATE1, and MATE2-K should be avoided including their administration at least within 2 weeks prior to the first study drug dose and throughout the study. Concomitant medication suspected of being a sensitive OATP1B1, OAT3, MATE1 and MATE2-K substrate with narrow therapeutic index must be approved by the Sponsor.

Current or anticipated use of drugs that are strong inhibitors of P-gp should be avoided, including their administration within at least 2 weeks prior to the first study drug dose and throughout the study. Concomitant medication with suspected strong P-gp inhibitory effect must be approved by the Sponsor.

If there is a question about a particular concomitant medication, discuss with the Medical Monitor.

5.4.1.1. Other Anti-Tumor or Investigational Drugs

Additional systemic anti-tumor therapy is not permitted while subjects are receiving study therapy.

5.4.2. Anti-Diarrheal, Anti-Emetic Therapy

Primary prophylaxis of diarrhea, nausea, and vomiting is not permitted in the first cycle in the Phase 1b portion of the study. Primary prophylaxis in subsequent cycles is at the Investigator's discretion. The choice of the prophylactic drug as well as the duration of treatment is up to the Investigator with Sponsor approval assuming there is no known or expected drug-drug interaction and assuming the drug is not included in the Prohibited Concomitant Medications section.

5.4.3. Anti-Inflammatory Therapy

Anti-inflammatory or narcotic analgesic may be offered as needed assuming there is no known or expected drug-drug interaction and assuming the drug is not included in the Concomitant Treatments section.

5.4.4. Corticosteroids

Chronic systemic corticosteroid use (prednisone \geq 12.5 mg/day or dexamethasone \geq 2 mg/day) for palliative or supportive purpose is not permitted (unless administered for adrenal insufficiency). Acute emergency administration, topical application, inhaled sprays, eyedrops or local injections are permitted.

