5. At least 1 measurable target lesion according to Response Evaluation Criteria in Solid Tumors (RECIST) v1.1. Subjects with central nervous system (CNS)-only measurable target lesion ≥ 5 mm as defined by RECIST v1.1 are eligible.
6. Required wash-out time that is related to prior therapies before starting repotrectinib combination treatment:
 - At least 14 days or 5 half-lives (whichever is shorter) must have elapsed after discontinuation of prior systemic therapy and all side effects from prior treatments must have resolved to grade ≤ 1 with the exception of alopecia.
 - At least 14 days must have elapsed after discontinuation of prior immunotherapy and all immune-related side effects from prior immunotherapy must have resolved to grade ≤ 1 .
7. Subjects with asymptomatic CNS metastases (treated or untreated) and/or asymptomatic leptomeningeal carcinomatosis are eligible to enroll if they satisfy the following criteria:
 - Subjects requiring steroids at a stable or decreasing dose (≤ 12 mg/day dexamethasone or equivalent) for at least 14 days.
 - Subjects on stable doses of levetiracetam (same dose for 14 days).
 - A minimum of 14 days must have elapsed from the completion of whole brain radiation treatment (WBRT) before the start of treatment, and all side effects (with the exception of alopecia) from WBRT are resolved to grade ≤ 1 .
 - A minimum of 7 days must have elapsed from the completion of stereotactic radiosurgery before the start of treatment and all side effects (with the exception of alopecia) from stereotactic radiosurgery are resolved to grade ≤ 1 .
8. Baseline laboratory values fulfilling the following requirements:

Absolute Neutrophils Count	$\geq 1,500/\text{mm}^3 (1.5 \times 10^9/\text{L})$
Platelets	$\geq 100,000/\text{mm}^3 (100 \times 10^9/\text{L})$ independent of platelets transfusion support for at least 7 days prior to dosing
Hemoglobin	$\geq 9.0 \text{ g/dL}$ independent of transfusion support for at least 7 days prior to dosing
Creatinine Clearance*	$> 40 \text{ mL/min}$

Total Serum Bilirubin	< 1.5 x ULN ($\leq 3.0 \times$ ULN for patients with Gilbert's Syndrome or liver metastases)
Liver Transaminases (AST/ALT)	< 2.5 x ULN; < 5 x ULN if liver metastases are present
Alkaline Phosphatase	< 2.5 x ULN; < 5 x ULN if liver and/or bone metastasis are present.
Serum Calcium, Magnesium and Potassium	Normal or CTCAE grade ≤ 1 with or without supplementation.

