Toxicity	CTCAE Grade 1*	CTCAE Grade 2*	CTCAE Grade 3	CTCAE Grade 4
Hematologic	Continue at same dose level.	Continue at same dose level.	Withhold dose until toxicity is grade ≤ 2 , or has returned to baseline, then resume treatment at the same dose level or reduce by one dose level ^{1,2} as per the Investigator's discretion. Grade 3 lymphopenia without other dose-limiting events (e.g., opportunistic infection) may continue study treatment without interruption.	Withhold dose until toxicity is grade ≤ 2 , or has returned to baseline, reduce the dose by one dose level ^{1,2} and resume treatment. Grade 4 lymphopenia without other dose-limiting events (e.g., opportunistic infection) may continue study treatment without interruption.
Non-Hematologic excluding dizziness, ataxia, and paresthesia	Continue at same dose level.	Continue at same dose level. For prolonged or intolerable CNS toxicity, withhold dose until toxicity is grade ≤ 1 or has returned to baseline, then reduce by one dose level ^{1,2} and resume treatment.	Withhold dose until toxicity is grade ≤ 1 or has returned to baseline.	Withhold dose until toxicity is grade ≤ 1 or has returned to baseline, then reduce by one dose level ^{1,2} and resume treatment; or discontinue treatment as per the Investigator's discretion.
ILD/Pneumonitis (occurred in the absence of disease progression, pulmonary embolism, positive cultures or radiation effect)	Asymptomatic, radiographic findings only: No need for dose adjustment. Initiate appropriate monitoring. Symptomatic: Withhold current dose until toxicity has returned to baseline. Rule out infection and consider initiating treatment with corticosteroids. Then resume treatment at the same dose. Discontinue permanently if pneumonitis recurs or if failure to recover after 28 days	Withhold current dose until toxicity has returned to baseline. Rule out infection and consider initiating treatment with corticosteroids. Then resume treatment at one dose level lower. Discontinue permanently if pneumonitis recurs or if failure to recover after 28 days of study treatment hold and steroid treatment.	Discontinue treatment permanently.	Discontinue treatment permanently.

Toxicity	CTCAE Grade 1*	CTCAE Grade 2*	CTCAE Grade 3	CTCAE Grade 4
	of study treatment hold and steroid treatment.			

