4.1. Subject Inclusion Criteria

Phase 1 AND Phase 2:

1. Subject must have a histologically or cytologically confirmed diagnosis of unresectable or metastatic solid tumor malignancy harboring a *KRAS* mutation.
 - Documented *KRAS*^{G12D} mutation as determined by a quantitative polymerase chain reaction (qPCR) or next-generation sequencing (NGS) test performed in a Clinical Laboratory Improvement Amendments (CLIA) laboratory or equivalently accredited diagnostic laboratory. Local tissue-based or liquid biopsy diagnostic testing will be permitted.
 - Adequate tumor tissue needs to be sent to the Sponsor designated central diagnostic laboratory for retrospective confirmation by a central diagnostic laboratory test selected by the Sponsor. See the Study Laboratory Manual for details.
2. Eastern Cooperative Oncology Group (ECOG) Performance Status 0–1
3. Age ≥ 18 (or as required by local regulation).
4. Willing and able to provide written institutional review board (IRB)/ethics committee (EC)-approved Informed Consent.
5. At least 1 measurable target lesion according to Response Evaluation Criteria in Solid Tumors (RECIST) v1.1. Subjects with central nervous system (CNS)-only measurable target lesion ≥ 5 mm as defined by RECIST v1.1 are eligible.
6. Required wash-out time that is related to prior therapies before starting repotrectinib combination treatment:
 - At least 14 days or 5 half-lives (whichever is shorter) must have elapsed after discontinuation of prior systemic therapy and all side effects from prior treatments must have resolved to grade ≤ 1 with the exception of alopecia.
 - At least 14 days must have elapsed after discontinuation of prior immunotherapy and all immune-related side effects from prior immunotherapy must have resolved to grade ≤ 1 .
7. Subjects with asymptomatic CNS metastases (treated or untreated) and/or asymptomatic leptomeningeal carcinomatosis are eligible to enroll if they satisfy the following criteria:
 - Subjects requiring steroids at a stable or decreasing dose (≤ 12 mg/day dexamethasone or equivalent) for at least 14 days.
 - Subjects on stable doses of levetiracetam (same dose for 14 days).
 - A minimum of 14 days must have elapsed from the completion of whole brain radiation treatment (WBRT) before the start of treatment, and all side effects (with the exception of alopecia) from WBRT are resolved to grade ≤ 1 .

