7.1. Screening and Eligibility

All subjects being considered for screening must provide informed consent prior to completing any study-specific procedures. A subject number will be assigned. After signing informed consent, subjects will be screened to confirm eligibility.

The following items must be completed as part of the screening procedures:

- An eligibility checklist must be completed for each subject and sent to the Sponsor for eligibility confirmation before enrollment
- Source documents of molecular pathology report, detailing the specific test that confirms KRAS mutational status, should be submitted for the Sponsor's approval of eligibility (refer to [Section 6.2](#) for additional information)
- Imaging studies (CT or MRI of the chest, abdomen, and pelvis and MRI of the brain) should be submitted for BICR assessment

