7.8.4. Supportive Care

Palliative and supportive care for disease-related symptoms may be administered at the Investigator's discretion and according to available American Society of Clinical Oncology (ASCO) guidelines.

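### Inclusion criterion 7 admits CNS subjects on stable dexamethasone up to 12 mg/day, but Section 5.4.4 bars chronic dexamethasone from 2 mg/day and excepts only adrenal insufficiency (minor)

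*Combined protocol and SAP*

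**What the plan says.** Two current provisions set dexamethasone limits.

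- **Entry.** Criterion 7, worded alike in the synopsis and in Section 4.1 and applying to both phases, states: "Subjects with asymptomatic CNS metastases (treated or untreated) and/or asymptomatic leptomeningeal carcinomatosis are eligible to enroll", subject to listed conditions. One condition is "Subjects requiring steroids at a stable or decreasing dose", capped at 12 mg/day dexamethasone or equivalent, for at least 14 days.
- **On study.** Section 5.4.4 addresses chronic systemic corticosteroids at prednisone 12.5 mg/day or more, or dexamethasone 2 mg/day or more. Such use "for palliative or supportive purpose is not permitted (unless administered for adrenal insufficiency"). The section then adds: "Acute emergency administration, topical application, inhaled sprays, eyedrops or local injections are permitted".

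Neither section refers to the other.

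**The concern.** The entry rule and the on-study rule concern the same drug in the same subject, and their limits differ widely. Criterion 7 recognises that some subjects with CNS disease require a steroid, and it accepts a dose that is merely stable. Nothing in it suggests that the dose should end at Cycle 1 Day 1. Section 5.4.4 then prohibits chronic use over most of the range that criterion 7 allows.

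Read literally, the investigator has two options for such a subject: reduce a steroid that the protocol itself treats as needed, or keep it and depart from the protocol. Subjects with CNS disease are an intended part of this study. CNS-only measurable disease is allowed under criterion 5, and intracranial response rate is a Phase 2 secondary endpoint, so the situation is foreseeable.

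**Working it through.** The plan gives no statistical figure to reproduce here. The check is a comparison of the steroid provisions, with one ratio.

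**Inputs**

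| Provision | Applies to | Dexamethasone limit |
|---|---|---|
| Criterion 7 (synopsis; Section 4.1) | Entry, asymptomatic CNS or leptomeningeal disease | Allowed up to and including 12 mg/day, stable or falling for at least 14 days |
| Section 5.4.4 | On study, chronic systemic use for palliation or support | Prohibited from 2 mg/day upward, except for adrenal insufficiency |

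**Step 1: the overlap.** For a stable dose *d* in mg/day that is continued on study:

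- *d* below 2: criterion 7 is met and Section 5.4.4 is not triggered, so there is no conflict.
- *d* from 2 to 12: criterion 7 is met, but Section 5.4.4 prohibits continuation.
- *d* above 12: criterion 7 is not met, so the question does not arise.

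Ratio of the limits: 12 / 2 = 6. This describes how far apart the rules are. It does not measure how many subjects are affected.

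**Step 2: does another provision resolve it?**

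- *Section 5.4.4, second sentence.* The further permitted uses are acute emergency, topical, inhaled, ocular and locally injected. None is a maintenance systemic dose.
- *Section 5.4.3.* Anti-inflammatory agents are allowed only if they are not listed under Concomitant Treatments, so this section defers to 5.4.4.
- *Table 4 (Section 3.5.1).* It tells the investigator to "consider initiating treatment with corticosteroids" only for ILD/pneumonitis, which is treatment of an adverse event.
- *Section 7.8.4.* "Palliative and supportive care for disease-related symptoms may be administered" at the Investigator's discretion. This is a general permission that does not mention steroids and does not displace a specific prohibition.
- *Section 5.4.1.* "If there is a question about a particular concomitant medication, discuss with the Medical Monitor". This is a route for asking and grants no exception.
- *Section 7.1.* "An eligibility checklist must be completed for each subject and sent to the Sponsor for eligibility confirmation before enrollment". A subject on a stable dose within the 12 mg/day ceiling meets criterion 7, so the Sponsor's check could properly pass that subject.

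No provision requires a taper below 2 mg/day before the first dose.

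**Step 3: do the terms of Section 5.4.4 cover this use?** The prohibition needs chronic use and a palliative or supportive purpose. The protocol does not define chronic. A required dose already held for 14 days or more, with no planned end, most naturally counts as chronic. Steroid given for CNS disease alongside study drug is not study treatment, and Section 5.4.1.1 rules out additional systemic anti-tumor therapy, so supportive is the ordinary description. A falling course may reasonably lie outside the prohibition, so the finding is confined to stable doses.

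**Step 4: reach into the analysis.** The Phase 2 primary efficacy analysis uses the FAS (Section 9.4.3), which is defined by dosing (Section 9.1.1), so a steroid deviation removes nobody from it. The Efficacy Evaluable set excludes major protocol violations that could affect efficacy (Section 9.1.2). A steroid deviation would matter there only if it were classed that way. That set serves Phase 1b efficacy and the Phase 2 sensitivity analysis. This route is possible, but nothing in the documents makes it likely.

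**The case against.** The strongest reply is that this is an ambiguity and not a contradiction. Section 5.4.4 applies only to chronic use for palliation or support. The first term is undefined, and no text says that steroids for asymptomatic CNS disease fall under the second. The rules also govern different times: a subject can satisfy criterion 7 at entry and then taper. Criterion 7 is the more specific provision, so a sensible site would probably treat it as the allowance. Any doubt would go to the Medical Monitor, and the Sponsor reviews every subject's eligibility.

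Much of this stands as mitigation. The missing definition is real, which is why falling doses are left out of the finding. Sponsor confirmation and Medical Monitor consultation make a harmful outcome less likely. The sixfold ratio is indeed not a measure of impact.

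It does not remove the conflict. Criterion 7 accepts a stable dose in a subject who requires it, so continuation past Day 1 is to be expected. Consultation is not a written exception. The drafters named adrenal insufficiency when they wanted an exemption, which makes an unstated one for CNS disease harder to infer. If sites can reasonably read the text either way, it still needs correcting.

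**Conclusion.** The point holds as a minor inconsistency. A subject on a stable dexamethasone dose of 2 to 12 mg/day may enter under criterion 7 and, as Section 5.4.4 is written, may not continue that dose. The entry ceiling is six times the on-study threshold.

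This rests on two readings: that a maintenance dose held for at least 14 days is chronic, and that steroid use for CNS disease is supportive. Both are the natural readings, but the protocol states neither. The number of subjects affected cannot be derived from the documents. The consequence is for patient care and protocol compliance. Sample size, the interim futility rule and the Phase 2 primary analysis are unaffected.

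**What to change.** Extend the exception in Section 5.4.4 so that it covers adrenal insufficiency and also steroid use for CNS metastases or leptomeningeal carcinomatosis as allowed under inclusion criterion 7. This costs one clause, carried in a protocol amendment with the IRB/IEC approval that Section 12.2 requires. It changes no eligibility limit and no analysis.

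Lowering the criterion 7 ceiling below 2 mg/day in the synopsis and Section 4.1 would also remove the conflict. It would, however, exclude CNS subjects who are now admitted, so it makes sense only if the sponsor really intends the 2 mg/day limit to govern.
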